9.2 Hip Outcome Score

The Hip Outcome Score (HOS)⁵ measures self-reported functional status through 28 items and two subscales that pertain to activities of daily living (ADLs) or higher-level activities such as those necessary to participate in sports. Patient-reported function, measured by the HOS, will be reported as mean differences with corresponding 95% CIs and p-values. (Tables 16, 17, and 18). Longitudinal models will be used to explore the effect of treatment group and time on the HOS patient-reported outcomes (Figures 10-12).

Table 16: Summary of HOS, According to Surgical Treatment (No Significant Interaction Between Implant Type and Supplementation Present)

Endpoint	Surgical Treatment X		Surgical Treatment Y		Total	
	N=	Mean (SD)	N=	Mean (SD)	N=	Adjusted Mean Difference (95% CI)
Post-op						
10 weeks						
3 months						
6 months						
9 months						
12 months						

Table 17: Summary of HOS, According to Nutritional Supplementation (No Significant Interaction Between Implant Type and Supplementation Present)

Endpoint	Nutritional Supplementation Treatment X		Nutritional Supplementation Treatment Y		Total	
	N=	Mean (SD)	N=	Mean (SD)	N=	Adjusted Mean Difference (95% CI)
Post-op						
10 weeks						
3 months						
6 months						
9 months						
12 months						

Figure 10: HOS Over Time by Surgical Treatment Group (No Significant Interaction Between Implant Type and Supplementation Present)

[figure not shown]

Figure 11: HOS Over Time by Nutritional Supplementation Group (No Significant Interaction Between Implant Type and Supplementation Present)

[figure not shown]
[figure not shown]

Table 18: Summary of HOS (Significant Interaction Between Implant Type and Supplementation Present)

Endpoint	Surgical Treatment X		Surgical Treatment Y		Nutritional Supplementation Treatment X		Nutritional Supplementation Treatment Y		Total	
	N=	Mean (SD)	N=	Mean (SD)	N=	Mean (SD)	N=	Mean (SD)	N=	Adjusted Mean Difference (95% CI)
Post-op										
10 weeks										
3 months										
6 months										
9 months										
12 months										

Figure 12: HOS Over Time by Treatment Group (Significant Interaction Between Implant Type and Supplementation Present)

9.3 Fracture Healing Complications

Table 19: Fracture Healing Complications

Fracture Healing Complication	Variable	Surgical Treatment X N=	Surgical Treatment Y N=	Nutritional Supplementation X N=	Nutritional Supplementation Y N=	Total N=
Wound Healing Problems	Adjudicated Data					
Infection - Superficial, n (%)	Adjudicated Data					
Infection – Deep, n (%)	Adjudicated Data					
Infection – Organ Space, n (%)	Adjudicated Data					
Implant Failure, n (%)	Adjudicated Data					
Implant Breakage, n (%)	Adjudicated Data					
Painful Hardware, n (%)	Adjudicated Data					
Peri-Prosthetic Fracture, n (%)	Adjudicated Data					
Other, n (%)	Adjudicated Data					

9.4 Radiographic Fracture Healing

Table 20: Radiographic Fracture Healing

Variable	Variable	Surgical Treatment X N=	Surgical Treatment Y N=	Nutritional Supplementation X N=	Nutritional Supplementation Y N=	Total N=
Time of Radiographic Fracture Healing, mean (SD) (months)	Adjudicated Data					
Time of Radiographic Healing of Ipsilateral Femoral Shaft Fracture, mean (SD) (months)	Adjudicated Data					

Figure 13: Kaplan-Meier Curves for Radiographic Fracture Healing (Significant Interaction Between Implant Type and Supplementation Present)

[figure not shown]

Figure 14: Kaplan-Meier Curves for Radiographic Fracture Healing by Surgical Treatment Group (No Significant Interaction Between Implant Type and Supplementation Present)

[figure not shown]

Figure 15: Kaplan-Meier Curves for Radiographic Fracture Healing by Nutritional Supplementation Group (No Significant Interaction Between Implant Type and Supplementation Present)

[figure not shown]

Figure 16: Kaplan-Meier Curves for Radiographic Healing of Ipsilateral Femoral Shaft Fracture (Significant Interaction Between Implant Type and Supplementation Present)

[figure not shown]

Figure 17: Kaplan-Meier Curves for Radiographic Healing of Ipsilateral Femoral Shaft Fracture by Surgical Treatment Group (No Significant Interaction Between Implant Type and Supplementation Present)

[figure not shown]
[figure not shown]

Figure 18: Kaplan-Meier Curves for Radiographic Healing of Ipsilateral Femoral Shaft Fracture by Nutritional Supplementation Group (No Significant Interaction Between Implant Type and Supplementation Present)

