4.8.2 Secondary Outcome

The secondary outcomes will include:

1. HRQL and patient-reported function as measured by the:
 - Short Form-12 (SF-12)⁴³ which measures self-reported quality of life through an 8-domain profile of functional health and well-being, physical and mental health summary measures and a preference-based health utility index.
 - Hip Outcome Score (HOS)⁴⁴ which measures self-reported functional status through 28 items and two sub-scales that pertain to activities of daily living (ADLs) or higher level activities such as those necessary to participate in sports.
2. Fracture healing complications: These will include wound healing problems, infection (superficial and deep), hardware failure, hardware breakage, painful hardware, and peri-prosthetic fracture.
3. Radiographic fracture healing: The date of healing will be determined by the Central Adjudication Committee (CAC). They will consider a fracture as healed when there is obliteration of the fracture line by newly formed bone along the cortices and within the trabecular bone on anterior-posterior and lateral radiographs.

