5.0 STATISTICAL PLAN

5.1 Sample Size Determination

The choice of sample size is based upon independent comparisons of the SHS versus multiple cancellous screw *AND* vitamin D supplementation versus placebo for the primary outcome (patient important outcomes). This is based on the assumption that both interventions will act independently. We will use an alpha level of 0.5 for the primary outcome and all statistical hypotheses will be 2-sided.

The preliminary sample size calculations are based on the limited published literature. As outlined in section 1.2, a pooled estimate from 18 published studies revealed a combined femoral head osteonecrosis and fracture nonunion incidence of 25%. In addition to femoral head osteonecrosis, the composite primary outcome includes other events such as re-operation and severe femoral neck malunion. These additional complications are expected to increase the composite event rate to approximately 40%; therefore, a conservative event rate of 30% is assumed in the cancellous screw and placebo groups.

The trial is powered for a RRR of 33% for each of the treatment comparisons: SHS versus multiple cancellous screws *AND* vitamin D₃ supplementation versus placebo. This RRR estimate is based on the best available literature and coincides with a 10% absolute risk reduction that was deemed to be clinically significant by over 500 surveyed surgeons.¹⁰ For the surgical comparison, Gardner et al²¹ and Chen et al²² reported an 86% and 100% RRR for reoperation using a SHS. Other more heterogeneous retrospective studies by Liporace et al²³ and Razik et al²⁴ suggest RRRs from SHS between 50-88% for osteonecrosis and 63% for nonunion (Section 1.3). Since these are uncontrolled retrospective studies, a conservative effect size estimate is maintained. With regard to the expected treatment effect of vitamin D supplementation, there are no clinical studies that quantify its efficacy to reduce fracture healing complications. Despite the lack of direct data, vitamin D supplementation following acute fractures has demonstrated a 40% increase in fracture callus density in human participants²⁹ and an 80% increase in mechanical strength in animal model.²⁸ Experimental evidence also suggests benefits of increased fracture area vascularity and improved healing that may also contribute to the treatment effect of vitamin D supplementation. We have also assumed the same RRR of 33% in the vitamin D treatment arm.

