5.2.3 Secondary Analyses

All secondary outcomes will be summarized using means and 95% confidence intervals, or percentages and 95% confidence intervals. Longitudinal models will be used to explore the effect of treatment group and time on the HOS and SF-12 patient-reported outcomes. **Table 4** shows the details for the analysis of secondary outcomes.

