Fracture healing complications	Rates of fracture healing complications will be lower in patients receiving SHS versus cancellous screws.	Rates of fracture healing complications will be lower in patients receiving vitamin D versus placebo.	Evidence of complications reported by patients or evident on X-Rays	Summary statistics of proportions Chi-square statistic with independent comparison for the surgical treatments and nutritional treatments
Fracture healing	Fractures will heal faster in patients receiving SHS versus cancellous screws.	Fractures will heal faster in patients receiving vitamin D supplementation.	A fracture will be considered as healed when there is obliteration of the fracture line by newly formed bone along the cortices and within the trabecular bone on anterior-posterior and lateral X-rays	Time to event analysis with treatment group as an independent variable

[figure not shown]
Table 5: Summary of Exploratory Analyses

Fracture/Surgical Characteristics	Hypothesis for Surgical Treatments	Hypothesis for Nutritional Supplementation	Outcome Measures	Method of Analysis
Undisplaced versus displaced femoral neck fractures	The magnitude of treatment effect favouring SHS will be higher in displaced fractures vs. undisplaced fractures	The magnitude of treatment effect favouring vitamin D will be higher in displaced fractures vs. undisplaced fractures	Composite primary outcome as above (reoperation, femoral head osteonecrosis, severe femoral neck malunion, and nonunion)	Logistic regression models with an interaction term between treatment and femoral neck displacement
Emergent (<8 hours) versus non-emergent (≥8 hours) internal fixation	The magnitude of treatment effect favouring SHS will be higher in fractures treated emergently vs. non-emergently.	Not Applicable	Composite primary outcome as above (reoperation, femoral head osteonecrosis, severe femoral neck malunion, and nonunion)	Logistic regression models with an interaction term between treatment and internal fixation type

Figure 1: Blood Supply to the Femoral Head

[figure not shown]
The femoral head and neck are perfused by a ring of small blood vessels. These fragile capsular vessels are most vulnerable to injury at the femoral neck and are frequently torn during the fracture. Disrupting the local blood supply leads to femoral head osteonecrosis (bone death) and femoral neck nonunion (the fracture does not heal)

Figure 2: Multiple Cancellous Screws

2a Diagram of screw fixation

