1.0 PURPOSE

The purpose of this statistical analysis plan (SAP) is to outline the primary statistical analyses for the Fixation using Alternative Implants for the Treatment of Hip Fractures (FAITH-2): A Multi-Centre 2x2 Factorial Randomized Trial Comparing Sliding Hip Screws versus Cancellous Screws AND Vitamin D versus Placebo on Patient Important Complications and Quality of Life in the Treatment of Young Adult (18-60) Femoral Neck Fractures manuscript. This SAP includes review of all data collected. The FAITH-2 Writing Committee will determine which data points will be included in the primary manuscript and supplemental documents. We will adhere to the CONSORT 2010 guideline when reporting the results of FAITH-2. Additional SAPs will be developed for secondary analyses.

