8.0 PRIMARY CLINICAL ENDPOINT

The primary analyses will first be completed using only blinded treatment groups. All outcome analyses will be performed using the intention to treat approach. The FAITH-2 study primary clinical endpoint is a composite of patient important outcomes that occur within the 12 months post-surgery follow-up period (**Table 9**). Specifically, these are limited to 1) re-operation, 2) femoral head osteonecrosis, 3) severe femoral neck malunion, and 4) nonunion.

The first analysis of clinical outcomes will be a Cox regression with main effects for implant type and supplementation, and the interaction between the two. If the interaction is not significant at $\alpha=0.05$ we will perform two independent comparisons between the treatment groups (SHS versus cancellous screws AND separately vitamin D₃ supplementation versus placebo) using the chi-square statistic and an alpha level of 0.05 for the composite of patient important outcomes (**Tables 10 and 11**).

If the interaction is significant we will keep this interaction term in all subsequent analyses, and present two hazard ratios (HRs) with 95% confidence intervals (CIs) for the surgical intervention and two HRs for the nutritional supplementation (i.e. We will report an HR for SHS versus cancellous screws in those who receive vitamin D, and a separate HR for SHS versus cancellous screws in those who receive placebo. We will also report an HR for vitamin D versus placebo in those who receive SHS, and a separate HR for vitamin D versus placebo in those who receive cancellous screws) The results will be summarized in **Table 12**. Kaplan-Meier curves will also be constructed.

Table 9: Primary Clinical Endpoint Components and Reasons for Secondary Procedures

Outcome	Definition
Unplanned Secondary Procedures (study event)	
Any unplanned surgery related to the treatment of the femoral neck fracture. Specific unplanned secondary procedures include:
 
 • Implant removal • Bone graft • Wound closure • Proximal femur osteotomy • Implant exchange – THA • Implant exchange – HA • Implant exchange – CS • Implant exchange – SHS • Implant exchange – Other IF • Soft tissue procedure • Dynamization • Osteochondroplasty

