Reasons for Secondary Procedures	
 • Shortening • Nonunion • Femoral head osteonecrosis • Deep infection • Superficial infection • Painful implant • Implant failure/breakage • Hip dislocation • Peri-prosthetic femur fracture • Hip instability • Wound healing problem • Screw penetration • Screw cut-out • Post traumatic arthritis • IT Fracture • Relieve pain
Femoral Head Necrosis	Any evidence of osteonecrosis on any follow-up medical imaging study (i.e., radiographs, magnetic resonance imaging (MRI), or other advanced imaging study)
Severe Femoral Neck Malunion	Fracture healing with femoral neck shortening of >10 mm in any plane on follow-up x-rays ¹
Nonunion	Failure of the fracture to progress towards healing defined as a Radiographic Union Score for Hip (RUSH) ^{2,3} score below a pre-determined threshold specific for nonunion at 6 months or greater post-injury.

Table 10: Primary Clinical Endpoint, According to Surgical Treatment (No Significant Interaction Between Implant Type and Supplementation Present)

End Point	Variable	Overall N=	Surgical Treatment X N=	Surgical Treatment Y N=	P-Value
Primary Clinical Endpoint of Re-operation					
Re-operation	Adjudicated Data				
Procedure for Nonunion Implant removal Bone graft Proximal femur osteotomy Implant exchange – THA Implant exchange – IF	Adjudicated Data				
Procedure for Femoral Head Osteonecrosis Implant removal Implant exchange – THA	Adjudicated Data				
Procedure for Deep Infection Wound closure Implant exchange – SHS Soft tissue procedure	Adjudicated Data				
Procedure for Painful Hardware Implant removal Bone graft Implant exchange – THA	Adjudicated Data				
Procedure for Screw Penetration Implant removal	Adjudicated Data				
Procedure for Post-Traumatic Arthritis Osteochondroplasty	Adjudicated Data				
Procedure for IT Fracture Implant exchange – IF	Adjudicated Data				
Procedure for Relieving Pain Implant exchange – THA	Adjudicated Data				
Femoral head osteonecrosis					
Femoral head osteonecrosis	Adjudicated Data				
Severe femoral neck malunion					
Severe femoral neck malunion	Adjudicated Data				
Nonunion					
Nonunion	Adjudicated Data				

Table 11: Primary Clinical Endpoint, According to Nutritional Supplementation (No Significant Interaction Between Implant Type and Supplementation Present)

End Point	Variable	Overall N=	Nutritional Supplementation X N=	Nutritional Supplementation Y N=	P-Value
Primary Clinical Endpoint of Re-operation					

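### SAP Table 20 describes neck healing time by a mean that exists only for healed fractures, and no rule says how a hip replaced before union enters the healing curves

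*Combined protocol and SAP*

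**What the plan says.** SAP 9.4 contains no prose. Its only numerical summary of neck healing is the first row of Table 20, "Time of Radiographic Fracture Healing, mean (SD) (months"), by surgical arm and by supplement arm. There is one N per arm, no row for number healed, no interval and no between-arm contrast. Figures 13-15 are titled as Kaplan-Meier curves for neck healing.

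Other sections bear on the same endpoint:

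- Protocol 4.8.2 defines the event: "The date of healing will be determined by the Central Adjudication Committee (CAC"), once the fracture line is obliterated on both radiographic views.
- Protocol Table 4 hypothesises faster healing with the sliding hip screw and with vitamin D, and plans "Time to event analysis with treatment group as an independent variable".
- Protocol 5.2.3 states: "All secondary outcomes will be summarized using means and 95% confidence intervals, or percentages and 95% confidence intervals".
- SAP 8.0 opens with "The first analysis of clinical outcomes will be a Cox regression with main effects for implant type and supplementation", plus their interaction. This may be meant to cover healing too.
- SAP 1.0 adds: "Additional SAPs will be developed for secondary analyses".

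Replacement of the hip is foreseen. SAP Table 9 lists total and hemi-arthroplasty among unplanned procedures, and SAP Table 10 has the row "Procedure for Nonunion Implant removal Bone graft Proximal femur osteotomy Implant exchange – THA". Protocol 1.1 notes that arthroplasty takes away the fractured area.

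**The concern.** There are two linked problems.

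First, a fracture that never unites, or is removed before it unites, has no healing date. The Table 20 mean is therefore taken over a subset defined after randomisation, by an outcome that both treatments are meant to change. Such a mean can miss a real difference in healing, or lean towards the worse arm if the additional healers in the better arm unite late.

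Second, a replaced hip can no longer heal. Neither document says whether it is censored at replacement, kept unhealed to month 12, or treated as a competing event. Plain Kaplan-Meier with censoring treats it as still able to heal at the same rate as the hips that remain. The healed proportion is then overstated, and most so in the arm with more early replacements.

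At stake is the reading of one secondary endpoint. Without a rule fixed in advance, the choice could be made after the data are seen.

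**Working it through.** **Figures in the plan.** The documents give no healing times, never-healed rates or replacement rates, so no figure for this endpoint can be reproduced. The 808 belongs to the primary composite and is used here only for precision. It reproduces with the continuity-corrected formula: 25% v 16.75%, two-sided alpha 0.05 and 80% power give 380 per arm uncorrected, and (380/4) x [1 + sqrt(1 + 4/(380 x 0.0825))]^2 = 404 per arm, or 808.

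**Assumed inputs.** Never healed: 10% to 15% in the worse arm. The nearest figure in the protocol is looser: 5.1 cites 18 studies that "revealed a combined femoral head osteonecrosis and fracture nonunion incidence of 25"%. Replaced before union: 3% to 7%, below the 20% rate for all re-operations in protocol 1.2.

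**1. The mean can miss a difference.** Let p be the proportion never healed and m the mean time among healers. Restricted mean time unhealed over 12 months = 12p + (1 - p)m. With m = 5 in both arms, Table 20 shows 5.0 v 5.0.

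- p = 10% v 6.7%: 5.700 v 5.469, difference 0.23 months.
- p = 15% v 10%: 6.050 v 5.700, difference 0.35 months.
- Over m = 4 to 6 the difference runs from 0.20 to 0.40 months.

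**2. The mean can point the wrong way.** At 90% v 93.3% healed, let the additional 3.3% unite at month x. The better arm's mean is (0.90 x 5 + 0.033x)/0.933, which is 5.07 at x = 7 and 5.18 at x = 10, against 5.00 in the worse arm.

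**3. Kaplan-Meier with replaced hips censored.** Healing times are gamma with mean 5 and SD 2 months, truncated at 12. Replacement is uniform over the stated window, and the remaining hips are unhealed at month 12. With healed proportion h and replaced proportion r, the curve reads 1 - exp{-integral of h f(t)/[1 - h F(t) - r U(t)] dt}, where f and F are the healing-time density and distribution function and U is the distribution function of replacement time.

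| Replacement window (months) | True 90%, 3% replaced | True 90%, 5% replaced | True 90%, 7% replaced | True 93.3%, 3% replaced |
|---|---|---|---|---|
| 2-9 | 92.2% | 93.9% | 95.9% | 95.8% |
| 4-11 | 91.6% | 92.8% | 94.4% | 95.2% |
| 6-12 | 91.0% | 91.8% | 92.8% | 94.6% |

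- True 90% v 93.3% (3.3 points), with 7% v 3% replaced: the curves show 95.8 - 95.9 = -0.1, 95.2 - 94.4 = 0.8 and 94.6 - 92.8 = 1.8 points.
- True 90% in both arms, with 7% v 3% replaced: false gaps of 95.9 - 92.2 = 3.7, 94.4 - 91.6 = 2.8 and 92.8 - 91.0 = 1.8 points, each favouring the arm with more replacements.
- If replaced hips are kept unhealed to month 12, the curves read the true 90% or 93.3%.

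**4. A second model, same mechanism.** Take a constant healing hazard of 0.30 per month from month 2 in both arms, and replacement at 0.01 v 0.03 per month (5.0% v 14.1% replaced unhealed). The censored curve gives 1 - exp(-0.30 x 10) = 95.0% in both arms. Cumulative incidence, 0.30/(0.30 + r) x exp(-2r) x [1 - exp(-10(0.30 + r))] with r here the monthly replacement hazard, gives 90.6% v 82.5%. The healed-only mean is 4.75 v 4.65 months, so the arm with more replacements looks faster.

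**5. Precision of a difference in proportion healed.** Half-width = 1.96 x sqrt{[h1(1 - h1) + h2(1 - h2)]/n}. At 404 per arm it is 3.8 points for 90% v 93.3% and 4.5 points for 85% v 90%. At the 43 per arm printed in the SAP Table 2 shell it is 11.7 and 13.9 points.

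**The case against.** Table 20 is descriptive. It has no P-value or effect column, unlike SAP Tables 10-12, and the planned comparison is the time-to-event analysis. A reader might infer that the arms are to be compared on healed-only means, or that no time-to-event analysis of healing exists. The documents do not support either: protocol Table 4 plans that analysis, the SAP plots the curves, and the Cox framework of SAP 8.0 may extend to healing. This stands. It makes the row a misleading description, not a wrong test.

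A reader might also infer that the planned curves are biased. That holds only if replaced hips are censored, and no text says they are. The bias also shrinks when replacement is late. Nonunion is defined only at 6 months or more after injury, so months 6-12 is the natural window for replacement on that ground, and there 1.8 of the 3.3 points survive. Replacement for other reasons can come earlier, so the whole range is shown.

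The hypothesis concerns speed, and a cause-specific hazard ratio answers that while censoring replaced hips. In step 4 the healing hazards really are equal. This is correct, but the curves will be read as proportions healed, and that reading fails.

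The shifts in the mean are small: 0.07 to 0.18 months in step 2, against a half-width of about 0.29 months for a difference in healed-only means at 404 per arm (SD 2). Nonunion is reported by arm in SAP Tables 10 and 11. Both points are fair, but those counts correct neither the mean nor the curves.

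Two other provisions do not close the gap. The single sentence on multiple imputation in SAP 10.0 names no outcome, and imputing a healing date for a removed fracture has no meaning. Further SAPs are promised, but Table 20 and Figures 13-15 are already in this one.

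**Conclusion.** The point holds in a limited form. The neck row of Table 20 conditions on healing and omits the number healed and any interval. The rule for hips replaced before union is missing from both documents. The text supports both statements with confidence.

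The size rests wholly on assumed rates and timing. If replaced hips are censored, a true 90% healed reads as about 91% to 96%, a 3.3-point difference as -0.1 to 1.8 points, and equal arms as differing by about 1.8 to 3.7 points. If they are kept unhealed to month 12, there is no such bias.

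Nothing here touches the primary composite or the 808. The change should be made because the summary misleads and the missing rule can decide how the curves read, not because a main conclusion is at risk.

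**What to change.** In SAP 9.4:

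- In the neck row of Table 20, replace mean (SD) with number healed and 12-month cumulative incidence of healing with 95% CI, and give the between-arm difference with 95% CI for each factor. Treat death and any re-operation that removes the unhealed fracture as competing events.
- Plot cumulative incidence of healing in Figures 13-15.
- Carry over the time-to-event model from protocol Table 4. Label its hazard ratio as cause-specific and read it beside the incidence difference, because that ratio alone still censors replaced hips.
- If a mean is kept, label it as among healed fractures only and give its n.

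The cost is one table row, three figure titles, a short paragraph and a small amount of extra analysis. Healing and re-operation are already adjudicated centrally (protocol 8.3). At about 43 per arm the incidence difference should be presented as descriptive only.
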